
Specific risks (although minor) may arise due to the nature of the survey and interview questions. The surveys will contain multiple measures of a psychological and development nature (e.g., stress, confidence, parenting ability). Responding to statements included in these measures may potentially alert parents to their behaviours and beliefs, and as a result may cause them some concerns.
	
At the end of the surveys parents will be instructed to speak to their case working social worker or VIG practitioner in the first instance if they have any concerns about the questions to which they responded, either in the surveys or in the interviews.
 
Dyads assigned to the intervention or control groups will both receive the usual LA-specific support provided to infants who are on a Child Protection or Child in Need plan, and their parents. Given that all these families will be open to children's social care, they will all have a social worker and be receiving this support.
 
The VIG practitioners involved are awarded a national recognized accreditation, proving they have reached the desired skills level. The training and supervision they receive is delivered by highly experienced VIG trainers. They have delivered similar training in many and various projects over the last 10 years, including in mother baby units, the NSPCC, CAMHS, Children's Services, Family Drug and Alcohol Courts, and Family Assessment units. Hence, practitioners will have the expertise to mitigate psychological risk or discomfort that may arise during the intervention.

Parents struggle to complete the online survey due to literacy issues, issues with understanding the survey measurements, or lack of access to internet
	
Telephone reminders will be carried out to non-responders and as part of this call interviewers will offer support in order for parents to complete the survey. Social workers and VIG practitioners will also be provided with a copy of the survey and information about how to support and encourage parents to participate.

Parents struggle to complete the online survey due to lack of English comprehension
	
Social workers are asked to confirm that the focal parent is sufficiently fluent in English to take part in the surveys.


Low response to the online surveys
	
Telephone reminders will be carried out to all non-responders. Social workers and VIG practitioners will be provided with information about the survey and asked to encourage parents to participate.
 
All parents in the trial will be invited to complete the follow-up survey, including those who do not respond to the baseline survey.
 
Parents in both the intervention and control groups will be offered a financial incentive of £5 to complete both the baseline and follow up surveys.

Low response to qualitative interviews
	
Social workers, delivery leads and trainers will be recruited with support from nominated leads for the intervention in each LA, as well as Babiest1st. Staff will be provided with accessible information about the IPE and why their participation is needed. Staff who are unable to participate during group sessions or site visits will be offered a one-to-one interview by telephone or video call at a time convenient to them.

	Interviews with parents will similarly be offered at a time which suits them and parents will be given a financial incentive of £30 as a thank you for their time.
Recruitment will be managed by each participating local authority and there is therefore a risk that areas do not take a consistent approach to recruitment and engage slightly different cohorts of parents.	Areas have been asked to appoint a recruitment lead to confirm eligibility before submitting recruited parents to IFF for randomisation and each lead will be provided with guidance materials on eligibility. Any notable differences between cohorts will be analysed upon completion of the baseline survey.
There remains considerable uncertainty about how the Covid-19 pandemic will play out over the delivery period.	This means we will need to be understanding and flexible in our dealings with Babies 1 st and with participating local authorities (LAs). This may mean needing to adapt our fieldwork approach and timings for process evaluation and we are happy to do this

Ethics & Participation

WWCSC's Research Ethics Committee have given ethical approval

Mat Met also submitted a separate ethics application (no. 33599) to the University's Arts and Humanities ethics committee in respect of their role as data processors. This was approved on 21/05/2021.

All staff participating in the IPE (including LA staff and Babies1st staff) will be provided with information upon recruitment explaining the research and how their data will be used. These documents will stress the voluntary nature of their participation. Verbal consent to participation and to recording of the interview will be collected before the interview begins.

Parents in the trial will be contacted by IFF's in-house recruitment team in order to encourage completion of the online survey and to be invited to take part in qualitative interviews. Recruiters will use an accessible information sheet to explain the purpose of the surveys and qualitative interviews to parents and the value of their participation. Recruiters will stress that participation is entirely voluntary and will not affect their dealings with their social worker or the social care system more broadly in anyway. Verbal consent to participation and to recording of the interview will be collected before the interview begins and parents will be informed that they can choose to withdraw their consent at any time.

Registration

This protocol will be published on WWCSC's website and also the [Open Science Framework \(OSF\)](#) website

Data Protection

IFF, as data controller, is registered with the Information Commissioner's Office for Data Protection under registration number Z5571698. IFF is accredited with ISO27001, the international standard for information security. We are fully compliant with GDPR and GDPR training is given to all staff members. All our storage, handling and processing of personal and sensitive data is conducted within the UK; and in line with ISO27001 (the international data security standard, with which IFF Research is accredited). All personal data is stored on our secure drive, which only the project team has access to. Data will be shared with Man Met using a password protected Excel document, transferred via IFF's secure file sharing

site. Man Met (as data processor) will keep all data secure from any unauthorised or accidental use, access, disclosure, damage, loss or destruction by using the University's Research Data Storage system.

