The Video Interaction Guidance (VIG) programme is being implemented between March 2021 (with intake from July 2021) and June 2022 in four English Local Authorities (LAs). VIG is a relationship based parenting intervention in which a VIG practitioner films a parent and child interacting in short, one-to-one sessions. By providing feedback on these sessions based on edited clips of better than usual moments, VIG aims to promote parental sensitivity, child attachment and longer term social and emotional development.

The intervention developer, Babies 1st, will train and supervise 21 VIG Practitioners across the four LAs. Practitioners will undertake the role in addition to their substantive role (e.g. social or family worker) and will each work with a minimum of six families (typically a focal parent and infant dyad) over eight sessions or more.

The programme is being evaluated by IFF Research and the Policy Evaluation and Research Unit (PERU) at Manchester Metropolitan University (Man Met). The evaluation comprises impact, implementation (process) and cost components. The impact study design is a pragmatic, multi-site, effectiveness trial, with individual family dyads allocated to intervention and control within sites, at random, on a 1:1 intervention to control basis. Families allocated to the intervention group will receive VIG in addition to their usual care; those in the control group will receive usual care only. All families will be asked to complete a baseline questionnaire containing psychometric measures prior to randomisation and also at four months post-randomisation. In addition, LAs will supply child protection outcomes from administrative data six months post-randomisation.

Intake will begin in August 2021 and will continue until the end of March 2022. Randomisation will begin in July 2021, and the intervention for all families will end by June 2022. An evaluation report will be published by the end of August 2022.

The evaluation includes a review point (September 2021) to allow for changes to the protocol and evaluation activity on account of factors which are currently unknown (e.g., the amount of dropout and proportion of parents requiring translation services or additional support to complete the survey). For further details see p.12.

Table of Contents

Background and Problem Statement	6
Intervention and Theory of Change	6
Logic Model	9
Interventions	10
Mechanisms	10
Outcomes	10
Impact Evaluation	11
Research Questions	11
Design	12

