How: The intervention will be delivered face-to-face. Social and family workers will meet with the focal parent and child. Some sessions may also include other family members (e.g. another parent) if suitable, although we expect the majority of intervention recipients to be parent-infant dyads, with the parent being the infant's mother in most cases. The intervention will also be delivered face-to-face wherever possible during any further Covid-19 lockdown periods. The Shared Reviews will either be face to face or online.

For the purposes of the evaluation, the 'focal parent' is defined as the infant's primary caregiver who will be the main recipient of the VIG intervention, and who will also complete the baseline and follow-up questionnaires.

Where: The intervention will focus on four areas:

- London Borough of Hounslow
- Stockport Borough Council
- Bath & North East Somerset Council
- 'Achieving for Children', which covers Kingston Council, Richmond Council and Windsor & Maidenhead Council

When and how much: 252 parent-infant dyads will be included in the trial, with the understanding that half will be randomly allocated to the intervention group, and the other half allocated to receiving 'support as usual' from their LA. Random assignment will be stratified at the LA level. Focal parents are most likely to be mothers but fathers will also be included where they are the only/primary care giver to the child. Parents will be recruited on an ongoing basis starting mid-July 2021, with delivery starting in August.

The 21 practitioners will see a minimum of six families each, for a minimum of eight sessions or more if needed, over the course of 12 months. The eight sessions consist of an initial

[figure not shown]
² O'Hara L, Smith ER, Barlow J, Livingstone N, Herath NINS, Wei Y, Spreckelsen TF, Macdonald G. *Video feedback for parental sensitivity and attachment security in children under five years*. Cochrane Database of Systematic Reviews 2019, Issue 11. Art. No.: CD012348. DOI: 10.1002/14651858.CD012348.pub2.

<https://www.cochranelibrary.com/cdsr/doi/10.1002/14651858.CD012348.pub2/full>

³ Kennedy, H., Macdonald & Whalley, P., (2016), 'Video Interaction Guidance, Providing an effective response for neglected children'. in Barlow, J et al., (2016) *Tackling child neglect: Research, policy and evidence-based practice*. Jessica Kingsley Publishers.

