The impact study design is a pragmatic, multi-site, effectiveness trial, with parent-infant dyads allocated to intervention and control within sites, at random, on a 1:1 basis. As a result, dyads are randomised within sites, which are local authorities, and the resulting data are clustered by site. Outcomes are recorded for the focal parent and focal child within dyads. There are four sites in total, with family dyads identified within each site by local intervention coordinators and then randomised to treatment and control using a randomised permuted block approach described more fully below.

Trained social workers are responsible, after training and discussions with Babies 1st, for identifying all eligible dyads that meet the inclusion criteria (with the exception of those for whom exclusion criteria apply), completing a referral form for each dyad and administering consent procedures. The referral form contains the following information:

- Focal parent’s contact details
- Focal parent’s age
- Focal child’s age
- Focal child’s gender
- Focal child subject to formal multi-disciplinary planning process (i.e. CP, CiN, Early Help Plan)?
- Other children in the household subject to formal multi-disciplinary plan?
- Ethnicity
- Focal parent’s care history
- Focal parent has other children taken into care?
- Does the focal parent smoke?

- Current accommodation
- Age focal parent finished full-time education
- Focal parent currently suffers from anxiety
- Focal parent currently suffers from depression
- Focal parent's alcohol consumption

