The participants in this study are families (expected to be represented mostly mother-baby dyads) within four English local authorities (LAs), recruited using convenience sampling. Formal expressions of interest were originally received from five LAs, and partnerships with four LAs meeting all eligibility criteria were finalised by mid-March 2021. Babies1st then trained social and family workers in each LA to become VIG Practitioners, assuming that each practitioner would work with around six dyads.

Table 2: Dyad recruitment and VIG practitioner numbers by site

Local Authority	Dyads recruited	VIG Practitioners
Achieving for Children (AfC)	120	10
Bath and North-East Somerset (BANES)	24	2
London Borough of Hounslow	24	2
Stockport	84	7

Criteria for including families in the study have been determined by local authorities in conjunction with Babies 1st, and are as follows:

- The family has a focal child aged 12 months or less; and
- The focal child is subject to either a Child in Need plan (CiN) or a Child Protection plan (CPP)

Families meeting these criteria will be eligible for inclusion unless they meet one or more of the following exclusion criteria:

- The focal parent does not speak or read English and does not have access to an interpreter (though this will be reviewed in September 2021 and the criteria may change);
- The referring social worker believes there to be a reason why the parent(s) cannot manage a psychological intervention at time of referral, due to:
 - serious mental health concerns;
 - serious physical health concerns;
 - being actively engaged in substance misuse.

Translation of the questionnaire instruments and provision of an interpreter for respondents who do not speak or read English were not planned due to budgetary constraints because VIG is primarily delivered in English. Furthermore the instruments the evaluation is using to measure the primary and secondary outcomes are not validated for the full range first languages spoken by parents. However, in September 2021 this will be reviewed following initial programme intake and through discussions with LAs. If there is a need for translations they will be undertaken.

Sample Size / Minimum Detectable Effect Size Calculations

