In line with WWCSA analytical guidance⁶, we will estimate the average effect of intention-to-treat (AITT) at the dyad (family) level using a two-sided test for statistical significance. We will obtain sample estimates of AITT via regression adjustment including an outcome measure derived from the baseline questionnaire as a covariate along with site fixed effects. The sample estimate of AITT will be converted from a regression coefficient into an effect size consistent with Glass's Delta for continuous outcomes. For binary outcomes, incident rates will be reported.

The table below presents the Minimum Detectable Effect Size (MDES) that the sample described is capable of detecting at the 95 per cent level of statistical significance and 80 per power. These calculations are considered to be provisional. They are made subject to an assessment of the degree of compliance with the intervention among the intervention group dyads. This assessment will be made at the Evaluation Review Point, which is discussed in more detail below. Should the assessment suggest that the assumptions made in these calculations are inaccurate, a revised protocol with updated calculations will be issued, with

⁶ What Works for Children's Social Care (2021). 'What Works for Children's Social Care Randomised Controlled Trial Statistical Analysis Guidance.'
<https://whatworks-csc.org.uk/wp-content/uploads/WWCSA-RCT-Statistical-Analysis-Guidance-V1.1-1.pdf>

further corrective actions take where necessary and possible within the general constraints faced by the trial.

MDES calculations account for the variation in sample sizes across local authorities by incorporating an estimate of cluster size based on the harmonic mean⁷ for the completed cases sample. Calculations were based on the assumed proportion of the variance in the outcome accounted for by the covariates in the fixed effects estimator (R^2). To establish the correlation coefficient, we identified the test-retest reliability for the MORS-SF warmth scale (0.70)⁸. This was then used to calculate the R^2 as the basis for the MDES.

MDES (Proportion of a Standard Deviation)		0.44
Proportion of Variance in Outcome Explained by Covariates⁹ (R^2)	Child	n/a
	Family (focal parent)	0.50
	Social Worker	n/a
Intracluster Correlations Coefficient (ICCs)	Family	n/a
	Social Worker	n/a
	Team	n/a
Alpha		0.05
Power		0.8
One-Sided or Two-Sided?¹⁰		Two-sided
Level of Intervention Clustering		Site
Average Site Size (harmonic mean)		21

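### Intervention dyads are nested in 21 VIG practitioners but the analysis recognises site clustering only, so any positive practitioner ICC makes the confidence intervals modestly too narrow

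*Protocol*

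**What the plan says.** On delivery, the Summary says that practitioners "will each work with a minimum of six families". The Intervention and Theory of Change section repeats it: "The 21 practitioners will see a minimum of six families each". The Participants section describes the training as "assuming that each practitioner would work with around six dyads", and its Table 2 lists 10 practitioners in Achieving for Children, 7 in Stockport, and 2 each in Bath and North East Somerset and in Hounslow. Of the comparison arm, the Summary says "those in the control group will receive usual care only".

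On clustering, the Design section says "dyads are randomised within sites, which are local authorities, and the resulting data are clustered by site". In the MDES table the row "Level of Intervention Clustering" reads Site, and the family, social worker and team ICCs are all n/a.

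On analysis, equation [1] under Primary Analysis contains site indicators, the treatment indicator, the baseline value of the outcome and one dyad-level error. Inference is by 95% confidence intervals, with a 500-replication bootstrap for Glass's Delta. Under Secondary Analysis, self-efficacy and parental stress are analysed by the same model and procedures. The sensitivity analyses cover treatment-by-site interaction, extra covariates, multiple imputation and extreme bounds. None refers to practitioners.

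**The concern.** About six intervention families share each practitioner, while control families have no VIG practitioner. Practitioners were trained for this programme, and the protocol expects them to differ: the qualitative methods section anticipates different experiences across the 21, and the process evaluation asks which social worker characteristics influence effectiveness. Outcomes of families seen by the same practitioner may therefore be correlated in one arm only.

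Site fixed effects remove differences between local authorities. They do not remove variation among the 10, 7, 2 and 2 practitioners within them. A model with independent dyad errors then understates the variance of the intervention mean, and hence of the treatment contrast. What is at stake is the coverage of the intervals for two co-primary and two secondary outcomes. No multiplicity correction is planned that might offset the excess error.

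**Working it through.** **Inputs from the protocol**
- 21 practitioners (Table 2)
- 71 intervention and 70 control completed cases (MDES table)
- 141 responders at both waves and 25 at follow-up only (Table 3)
- R² = 0.50, two-sided alpha 0.05, power 0.80, average site size 21 (MDES table)

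**Assumed.** The practitioner ICC, on the residual scale, is taken as 0.02, 0.05 and 0.10. The protocol gives no value.

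**Step 1: reproduce the stated MDES.** For four fixed sites of average size 21 there are 4 × 21 = 84 dyads.
- MDES = (1.960 + 0.842) × √[(1 − 0.50) / (0.25 × 84)] = 2.802 × 0.1543 = 0.432.
- With t quantiles it is 0.438. With R² = 0.70² = 0.49 it is 0.437 (normal) or 0.442 (t).
- The stated 0.44 is therefore reproduced on 84 dyads with no practitioner ICC.
- On the 141 dyads shown in the same table, the formula gives 2.802 × √[0.50 / (0.25 × 141)] = 0.334.

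**Step 2: variance under partial nesting.** With m intervention dyads per practitioner, the intervention-arm design effect is DE = 1 + (m − 1) × ICC. The control arm keeps 1. With nearly equal arms, the ratio of true to planned standard error is √[(DE + 1)/2], and the type I error is 2 × P(Z > 1.96 / ratio).

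Completed cases, m = 71/21 = 3.38:

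| ICC | DE | SE ratio | Type I error | Coverage |
|---|---|---|---|---|
| 0.02 | 1.048 | 1.012 | 5.3% | 94.7% |
| 0.05 | 1.119 | 1.029 | 5.7% | 94.3% |
| 0.10 | 1.238 | 1.058 | 6.4% | 93.6% |

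A simulation of the site-adjusted regression (without the baseline covariate), with practitioners laid out 10/7/2/2, gave type I errors of about 5.3%, 5.5% to 5.9%, and 6.2% to 6.3% at the three ICCs. This agrees with the formula.

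**Step 3: imputed analysis.** Observed follow-ups number 141 + 25 = 166, or 83 per arm if split evenly, so m = 83/21 = 3.95. DE is 1.059, 1.148 and 1.295. The SE ratios are 1.015, 1.036 and 1.071.

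**Step 4: MDES with nesting on 141 completed cases.** It is 0.338, 0.343 and 0.353 at the three ICCs. It reaches 0.44 only at an ICC of about 0.63.

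**Step 5: does the remedy hold its level?** Practitioner-clustered standard errors with each control dyad as its own cluster gave about 6% type I error against a normal reference, and roughly 4.5% to 5% against t on 20 df. The small-sample reference is needed.

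**The case against.** **The size is small and depends on an assumption.** This stands. The direction requires a positive ICC, and none is given. Expected missingness is far larger: 252 − 141 = 111 dyads without both questionnaires.

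**The variance estimator and bootstrap unit may belong to a statistical analysis plan.** This stands in part. The protocol names neither a variance estimator nor a resampling unit, so it cannot be said to bootstrap individual dyads. It does fix the model, name site as the level of clustering and list the sensitivity analyses, and practitioners appear in none of these.

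**The estimand may be limited to this sample.** The primary analysis targets a sample average effect, with sites fixed because they are a convenience sample. If inference were confined to these 21 practitioners, the shortfall would be smaller. The protocol makes that choice for sites and does not state it for practitioners.

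**Controls may share workers too.** All families have a social worker, so some usual-care clustering is possible in both arms. The protocol gives no caseload figures to quantify it. It would not remove the VIG practitioner effect, which exists in one arm only.

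**Stronger readings to avoid.** A reader might infer that imputation makes matters much worse, because all 126 intervention dyads (six per practitioner) enter. It does not: the described imputation model contains no practitioner term, so imputed outcomes bring no practitioner correlation, and about four observed outcomes per practitioner is the relevant figure. A reader might also infer that the MDES of 0.44 is too optimistic. Steps 1 and 4 show otherwise, because it corresponds to 84 dyads when 141 are expected.

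**Conclusion.** The point holds as a modest, conditional defect. The nesting is documented and the specified analysis ignores it. For assumed ICCs of 0.02 to 0.10, the true standard error exceeds the planned one by 1.2% to 5.8% in completed cases and by about 1.5% to 7.1% in the imputed analysis. Nominal 95% intervals cover about 93.6% to 94.7% in completed cases. This rests on equal caseloads, independent control dyads and an ICC on the residual scale. Unequal caseloads would increase the effect. So would practitioner effects arising after baseline: 0.05 of raw variance is about 0.05/0.51 = 0.10 of residual variance when R² is 0.49. The MDES omits practitioner clustering, but the stated value remains conservative for the expected sample.

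**What to change.** - **Record** the delivering practitioner for each intervention dyad at allocation. The listed referral-form fields do not include it, and exposure records are to be sought only if possible, so the nesting may not be recoverable later.
- **Keep** equation [1] with site fixed effects. Add either a practitioner random effect in the intervention arm only (a partially nested mixed model), or practitioner-clustered standard errors with each control dyad as its own cluster. In both cases use a small-sample correction, such as t on about 20 df, Satterthwaite or Kenward-Roger.
- **Derive the Glass's Delta interval** from that standard error, or from a bootstrap that does not resample practitioners within the two-practitioner sites. Resampling two clusters roughly halves the estimated variance there.
- **Show the MDES over a range of practitioner ICCs** at the September 2021 review, where the power calculations are already to be updated.

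The cost is one ID field, one analysis option and slightly wider intervals.
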